10.0 Procedures Involved

10.1 *Provide a description of **all research procedures or activities** being performed and when they are performed once a subject is screened and determined to be eligible. Provide as much detail as possible.*

NOTE: This should serve as a blueprint for your study and include enough detail so that another investigator could pick up your protocol and replicate the research. For studies that have multiple or complex visits or procedures, consider the addition of a schedule of events table in in your response.

Response:

Following informed consent, in order to rule-out sleep apnea as a confounder, all eligible participants will be offered screening for sleep apnea with the ApneaLink Plus for one night. Following a negative screen for sleep apnea, demographics, diagnoses, treatments, comorbidities, etc. will be extracted from the Electronic Health Record (EHR) using the Medical Record Review Questionnaire (to verify certain self-report data); beliefs about sleep will be determined by Dysfunctional Beliefs and Attitudes about Sleep; mood, anxiety and depression will be measured with Hospital Anxiety and Depression Scale; pain and quality of life will be determined by Functional Assessment of Cancer Therapy-G; sleep quality will be measured with Pittsburgh Sleep Quality Index; daily sleep will be assessed with 7-day sleep diary; objective sleep will be evaluated with 7-day actigraph; fatigue will be assessed with Profile of Mood States; and daytime sleepiness will be determined by the Epworth Sleepiness Scale (Johns 1991).

One week, after baseline assessments, each participant will be randomized by the biostatistician. Participants will then be scheduled for either the brief behavioral therapy for insomnia (BBTI) session (experiment) or the healthy eating program (HEP) session (control). Each intervention is approximately 45-minutes and will be delivered in the clinical setting, online teaching or home.

At the end of the interventions, each participant will be provided weekly sleep diaries to complete for 2-weeks and arrange for 2-follow up telephone calls using the Telephone Follow Up Script (attached). Each telephone contact will begin by reminding participants that their participation is voluntary and they may skip items they wish. Telephone

contacts are not recorded, but the research assistant will orally ask the participant to respond to the questions in the Telephone Follow Up Script and record responses as described in 10.2. Study packets with questionnaires will be repeated approximately one-month, 3-months and 12-months after the intervention. Patient Evaluation Questionnaire will be administered 1-month and at end of study. Following the one-month data collection, the interventionist will contact participants to provide feedback on sleep diary data. In addition, two REDCap emails at 6-months and 9-months from the intervention will be sent to ensure patient safety and encourage participant retention. The emails will ask the participants to answer a safety question we currently ask at each previous data collection with a "Yes" or "No" answer: Do you find that your sleepiness is bad enough that you are at risk of falling asleep while driving or doing something hazardous or harmful? Additionally, we will ask 2 questions from the Sleep Diary about their sleep: Please rate over the past week: Restful sleep 0-4 (4=excellent) and Sleep quality 0-4 (4=excellent).

10.2 Describe what data will be collected.

NOTE: For studies with multiple data collection points or long-term follow up, consider the addition of a schedule or table in your response.

Response:

Data include apnea/hypopnea index, movement (i.e. actigraphs), self-report sleep diaries and sleep, mood and quality of life questionnaires. Two-semi-structured telephone interviews will be conducted. For each interview, the data will be the participant's oral responses to the questions of the interview instruments as recorded in the research assistant's handwritten notes.

Table 3. Study Variables, Measures, and Time Frames

Variable	Measure	Pr e	1- Mon th	3- Mont hs	6- Mont hs	9- Mont hs	12- Mont hs
Predisposing factors Sleep history Age, sex, race/ethnicity	Holland Sleep Disorders Questionnaire /ApneaLink Plus Medical Record Review Questionnaire	X X					
Precipitating factors Cancer stage/treatment	Medical Record Review Questionnaire	X					

Alcohol/nicotine/caffeine Comorbidities Medications							
Perpetuating factors Beliefs about sleep	Dysfunctional Beliefs and Attitudes about Sleep	X	X	X			X
Neurocognitive factors Symptoms: depression, anxiety and pain	Hospital Anxiety and Depression Scale (anxiety and depression), Functional Assessment of Cancer Therapy (pain)	X X	X X	X X			X X
Insomnia characteristics Subjective sleep (insomnia severity, sleep quality) Objective sleep (sleep efficiency)	Insomnia Severity Index, Pittsburgh Sleep Quality Index, Sleep diary (daily) Actigraphy-Actiwatch Spectrum Safety emails	X X X	X X X	X X		X X	X
Vulnerability for physical-psychiatric problems Fatigue Sleepiness Disrupted mood Functional status Quality of life	Profile of Mood States Fatigue Subscale Epworth Sleepiness Scale Hospital Anxiety and Depression Scale Functional Assessment of Cancer Therapy-G Functional Assessment of Cancer Therapy-G	X X X X X	X X X X X	X X X X X			X X X X X
Telephone Follow Up	Script		X				
Patient Evaluation Questionnaire	Perceptions of study		X				X

	effectiveness						
--	---------------	--	--	--	--	--	--

10.3 List any instruments or measurement tools used to collect data (e.g. questionnaire, interview guide, validated instrument, data collection form).
 Include copies of these documents with your submission.

Response:

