1.0 Objectives

1.1 *Describe the purpose, specific aims, or objectives of this research.*

Response:

Specific Aim 1: To determine the efficacy of Brief Behavioral Treatment for Insomnia (BBTI), experimental condition, compared to Healthy Eating Program (HEP), attention control, on insomnia severity in cancer survivors with insomnia.

Specific Aim 2: To determine predictors for efficacy of BBTI.

Specific Aim 3: To evaluate BBTI implementation with a focus on characterization of the patient- and provider-level facilitators and barriers.

1.2 *State the hypotheses to be tested, if applicable.*

NOTE: A hypothesis is a specific, testable prediction about what you expect to happen in your study that corresponds with your above listed objectives.

Response:

Hypothesis 1: Participants receiving BBTI will exhibit significant and durable improvement in insomnia severity index (key variable), sleep quality, mood, and functional status and quality of life measures over HEP.

Hypothesis 2: Selective demographics (older age), disease stage (stage I), treatment-related (surgery only), mood (nondepressed) and positive beliefs about sleep (needing less than 8-hours of sleep) will predict BBTI efficacy.

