Taken together these previous studies confirm that insomnia was common in this homogeneous sample of cancer survivors. BBTI significantly reduced insomnia and improved quality and QOL at the post treatment measure. However, durability in the efficacy of BBTI was not assessed at 3-months or 12-months post-treatment. Additionally, current sleep literature does not include studies using BBTI in heterogeneous samples of cancer survivors with insomnia. This research team has the knowledge and experience to conduct and deliver the proposed RCT. In fact, this team includes researchers with expertise in the areas of nursing, medical oncology, pulmonary/sleep medicine and biostatistics. The NIH-funded PI is an advanced practice nurse with more than 20 years of clinical experience and 15 years of cancer-related fatigue, sleep and circadian rhythms and QOL research. The PI is collaborating with [name], DNS, RN, Professor and Chair of Biobehavioral Health and Clinical Sciences, University at

Buffalo, School of Nursing, a qualitative researcher, [name], a pulmonologist, sleep clinician and Co-Director of the University at Buffalo Sleep Fellowship Program; [name], Professor of Oncology, Roswell Park Comprehensive Care Center (RPCCC) and [name], Professor and Chair, Department of Biostatistics, University at Buffalo. The PI has an established record of collaboration with clinicians and researchers from RPCCC and the University at Buffalo, NY.

3.2 *Include complete citations or references.*

Response:

1. Institute of Medicine CoSMaR, Board on Health Sciences, Policy. *Sleep disorders and sleep deprivation: an unmet public health problem.* Washington, DC: National Academy of Sciences; 2006.
2. Ohayon MM. *Epidemiology of insomnia: what we know and what we still need to learn.* Sleep Med Rev. 2002;6(2):97-111. PubMed PMID: 12531146.

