4.0 Study Design

4.1 *Describe and explain the study design (e.g. case-control, cross-sectional, ethnographic, experimental, interventional, longitudinal, observational).*

Response:

This is a longitudinal, randomized, efficacy trial. The experimental intervention, BBTI (attached), is being used to help participants with insomnia to sleep better. To receive this treatment, participants need to be enrolled in the study. The attention control intervention, HEP (attached), is not expected to improve sleep.

Baseline measures will be obtained prior to the intervention.

All of the multi-components of BBTI will be delivered individually in the clinic setting or online during a 45-minute session.

Outcome measures will be completed 1-month and again at 3-months and 12-months post-intervention. Each participant will complete one-week of: 1) Sleep diaries; 2) wrist actigraphy; and 3) a study packet with questionnaires on insomnia severity, sleep quality, insomnia symptoms, and beliefs about sleep, functional performance and quality of life. Additionally, two REDCap emails at 6-months and 9-months from the intervention will be sent to ensure patient safety and encourage participant retention. The emails will ask the participants to answer a safety question we currently ask at each previous data collection with a "Yes" or "No"

answer: Do you find that your sleepiness is bad enough that you are at risk of falling asleep while driving or doing something hazardous or harmful?

Additionally, we will ask 2 questions from the Sleep Diary about their sleep: Please rate over the past week: Restful sleep 0-4 (4=excellent) and Sleep quality 0-4 (4=excellent).

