11.0 Study Timelines

11.1 Describe the anticipated duration needed to enroll all study subjects.

Response:

The enrollment period is planned for 3 years.

11.2 Describe the duration of an individual subject's participation in the study. Include length of study visits, and overall study follow-up time.

Response:

One week of data collection at home by the participant. Randomization to an intervention involving one 45-minute individual session with two 30-minute telephone calls delivered 1- and 2-weeks after the intervention concluding with a 1-month, 3-month and 12-month follow up in person or by mail. Following the one-month data collection, the interventionist will contact participants to provide feedback on BBTI and PASS programs.

Participation will involve approximately 11-12 hours over a 13-month time period.

11.3 Describe the estimated duration for the investigators to complete this study (i.e. all data is collected and all analyses have been completed).

Response:

The estimated duration for the investigators to complete this study is 5 years.

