17.0 Data Management and Analysis

17.1 *Describe the data analysis plan, including any statistical procedures. This section applies to both quantitative and qualitative analysis.*

Response:

Specific Aim 1. The primary analyses involve the statistical assessment of Insomnia Severity Index (ISI) at 1 month and will be based on an analysis of covariance (ANCOVA) model. In taking this approach, we fit the dependent variable as a linear function of independent variables randomized treatment assignment, patient cancer type, the interaction between treatment assignment and cancer type, and baseline ISI level. Rather than utilizing the null distribution associated with the classic F-test for overall treatment differences within the ANCOVA framework, which is dependent on the validity of distributional assumptions, an exact permutation testing approach will be utilized. The randomization mechanism at work is a crucial component in this study in that it will be used to create the randomization distribution by which statistical significance will be determined. For more on this approach see Gail, Tan, and Piantadosi (1988)(120). Reported p-values will be obtained from the permutation distributions of the test statistics based on 10,000 Monte Carlo simulations. As additional analyses, subject covariates will be included as independent variables.

The interaction of treatment group and subject covariates may also be examined in a secondary fashion in order to identify possible differential effects of treatment. The analysis of secondary outcomes will proceed in a similar fashion. All statistical tests will be two-sided and tested at a 0.05 nominal significance level.

Specific Aim 2. Standard multiple regression will be used to determine predictors of efficacious response to BBTI. Standard diagnostic plots will be used to assess model fit and transformations of variables may be considered in order to meet statistical assumptions.

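### Does the feedback contact after month 1, worded differently in Sections 10.1 and 11.2, undermine the 3- and 12-month comparison with HEP?

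*Combined protocol and SAP*

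**What the plan says.** Two sections describe a contact by the interventionist once the one-month data are in. Section 10.1: "Following the one-month data collection, the interventionist will contact participants to provide feedback on sleep diary data". Section 11.2, after the same opening: "the interventionist will contact participants to provide feedback on BBTI and PASS programs". Neither names an arm or gives a date beyond that opening.

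Both arms have diary data. Section 10.1 says that after the session "each participant will be provided weekly sleep diaries to complete for 2-weeks", and Section 4.1 says of the outcome assessments: "Each participant will complete one-week of: 1) Sleep diaries; 2) wrist actigraphy". On the control, Section 4.1 says: "The attention control intervention, HEP (attached), is not expected to improve sleep".

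On timing, Section 17.1 states: "The primary analyses involve the statistical assessment of Insomnia Severity Index (ISI) at 1 month". Hypothesis 1 in Section 1.2 also claims that the advantage over HEP lasts. Section 3.1 says of the earlier work that "durability in the efficacy of BBTI was not assessed at 3-months or 12-months post-treatment".

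Section 10.3 lists the BBTI and HEP presentation and the telephone follow-up scripts as attachments. They are not part of the supplied text.

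**The concern.** An attention control should match the experimental arm for time and contact without delivering the active ingredient. Individual feedback on one's own sleep record, given by the interventionist, could act as a light form of sleep treatment. If HEP participants receive it soon after month 1, the control is no longer inert for two of the three post-intervention assessments. Those two, at 3 and 12 months, carry the durability claim and are the ones the pilot left open. A real lasting benefit of BBTI could then be understated or missed.

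Section 11.2 adds doubt. It gives the feedback a different subject and names a programme that does not otherwise exist in the text. A reader cannot tell from the two sentences alone what a HEP participant hears after month 1.

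**Working it through.** **1. Who is contacted.** Both sections say participants, without restriction. On either reading the two arms get the same contact, so there is no imbalance in attention.

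**2. What is said.** In 10.1 the subject is diary data; in 11.2 it is the programmes. One call can cover both, so the sentences differ without excluding each other. The only programmes elsewhere in the text are BBTI and HEP. Section 11.2 pairs PASS with BBTI, so HEP is the natural referent. On that reading, each arm hears about its own programme.

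**3. When.** Outcomes are assessed at 1, 3 and 12 months. The contact follows the one-month data collection, so the primary ISI value is recorded first and cannot be affected. If the contact is made promptly, it falls about 3 − 1 = 2 months before one later assessment and 12 − 1 = 11 months before the other. The documents do not state that it precedes month 3; that is the natural inference.

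**4. Direction.** Let D be the later ISI difference (HEP minus BBTI) without the contact. Let h and b be the ISI reductions that the contact produces in HEP and BBTI. The observed difference is D − (h − b).

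- h = b (including both zero): the comparison is unchanged.
- h > b, the case feared here: the difference shrinks, which makes a durability claim harder to reach.
- b > h: the difference grows, but the contact is then part of the BBTI package being tested.

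The mechanism that raises the worry therefore cannot produce a false claim in favour of BBTI.

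**5. Size.** Section 17.2 gives SD 4.8, difference 3, 90% power, 55 per group and 30% dropout; Section 17.1 gives two-sided 0.05. These figures reproduce:

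- n = 2 × (1.960 + 1.282)² × 4.8² / 3² = 53.8, so 54 per group; the t-test version gives 54.8, so 55.
- 110 / 0.70 = 157.1, so 158 in two equal arms.

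The documents give no figure for h or b, and no planned difference at 3 or 12 months. Purely as an assumption, take a true later difference of 3 and 55 per group. The standard error is 4.8 × √(2/55) = 0.915, and power is Φ(difference / 0.915 − 1.96):

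| Assumed shrinkage | Difference | Power |
|---|---|---|
| 0% | 3.0 | 0.91 |
| 10% | 2.7 | 0.84 |
| 20% | 2.4 | 0.75 |
| 30% | 2.1 | 0.63 |
| 50% | 1.5 | 0.37 |

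The table shows what would be lost if shrinkage occurred. Nothing in the documents favours any row, and the first is as consistent with them as the others.

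**6. What a restriction would cost.** The substantive alternative is to withhold diary feedback from HEP until the 12-month data are in. Section 9.1 refers to previous patients and Section 19.2 to an email check being added, so the trial appears to be under way. A switch now would give earlier and later participants different contacts. It would also make the content of the contact differ by arm. Section 21.1 uses the diaries to monitor daytime sleepiness, with no arm restriction, so a ban on diary feedback would have to be separated from safety communication.

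**The case for a change.** The best case for a change is that Section 10.1 is where procedures should be spelled out well enough for another team to repeat them, and here it is not specific. Durability is a stated aim. Section 22.1 expects little direct benefit for controls, which sits awkwardly with individual sleep feedback to them. A missed durable effect is a real loss even though it is a conservative one, and settling two sentences costs almost nothing.

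Part of this stands. The wording does differ, PASS is undefined, and no supplied section sets the content by arm. Anyone reporting the 3- and 12-month results should describe the contact as it was delivered.

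The step from there to a defect in the design does not stand. No section says that the feedback includes advice; it may be a plain report of what was recorded. The low expectation of benefit in HEP suggests that the contact was not meant as sleep treatment there. The attached scripts may already set the content.

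**Conclusion.** No change to the plan is needed. The mismatch between 10.1 and 11.2 is a clerical slip, to be reconciled along with the PASS label at the next routine edit; this alters neither the design nor the analysis. Giving both arms the same kind of contact is a fair trade-off: it keeps attention balanced and accepts a possible, unmeasured weakening of the later contrast. Withholding diary feedback from HEP would be a different design preference, with a sure cost in consistency and an unproven gain.

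The effect on the primary 1-month ISI analysis is zero. The effect at 3 and 12 months is unknown and may be nil; under the feared mechanism it works against BBTI.

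This rests on three assumptions: that PASS means HEP or is otherwise a leftover name, that both arms are contacted alike as both sections say, and that the feedback is not active sleep coaching. Delivery records or scripts showing contact in one arm only, or sleep coaching given to HEP, would reopen the question for the two later assessments, though not for the primary one.

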Attachment – Participant Eligibility Screening Form
 Attachment – Eligibility Recruitment Script
 Attachment – Holland Sleep Disorders Questionnaire
 Attachment – ApneaLink Plus
 Attachment – Medical Record Review Questionnaire
 Attachment – Dysfunctional Beliefs and Attitudes about Sleep Scale
 Attachment – Hospital Anxiety and Depression Scale
 Attachment – Functional Assessment of Cancer Therapy – General
 Attachment – Insomnia Severity Index (ISI)
 Attachment – Sleep Diary
 Attachment – Actigraphy=Actiwatch Spectrum
 Attachment – Pittsburgh Sleep Quality Index (PSQI)
 Attachment – Profile Mood States Fatigue Subscale (POMS-F)
 Attachment – Epworth Sleepiness Scale (ESS)
 Attachment -Presentation: Brief Behavioral Treatment Insomnia (BBTI) and Healthy Eating Program (HEP)
 Attachment -Phone Follow Up Scripts
 Attachment -Patient Evaluation Questionnaire

10.4 Describe any source records that will be used to collect data about subjects (e.g. school records, electronic medical records).

Response:

Electronic health record at Roswell Park Comprehensive Cancer Center

10.5 Indicate whether or not **individual** subject results, such as results of investigational diagnostic tests, genetic tests, or incidental findings will be shared with subjects or others (e.g., the subject's primary care physician) and if so, describe how these will be shared.

Response:

If the results of ApneaLink Plus reveals AHI >15, the participant will be provided 2 copies of the ApneaLink Plus report: one for themselves and a copy for their provider.

10.6 Indicate whether or not study results will be shared with subjects or others, and if so, describe how these will be shared.

Response:

Results of the study will be published via abstract, poster and manuscript to journals. All results will be aggregated and de-identified.

11.0 Study Timelines

11.1 Describe the anticipated duration needed to enroll all study subjects.

Response:

The enrollment period is planned for 3 years.

11.2 Describe the duration of an individual subject's participation in the study. Include length of study visits, and overall study follow-up time.

Response:

One week of data collection at home by the participant. Randomization to an intervention involving one 45-minute individual session with two 30-minute telephone calls delivered 1- and 2-weeks after the intervention concluding with a 1-month, 3-month and 12-month follow up in person or by mail. Following the one-month data collection, the interventionist will contact participants to provide feedback on BBTI and PASS programs.

Participation will involve approximately 11-12 hours over a 13-month time period.

11.3 Describe the estimated duration for the investigators to complete this study (i.e. all data is collected and all analyses have been completed).

Response:

The estimated duration for the investigators to complete this study is 5 years.

